## 1. Background and Significance

Over 5 million central venous catheters (CVCs) are inserted annually in the United States. CVCs improve quality of life in cancer patients by allowing safe administration of chemotherapy and easy access for phlebotomy. Despite these benefits, long-term presence of CVCs are associated with infectious and thrombotic risks. The incidence of catheter-related thrombosis (CRT), or thrombosis in the vein housing the catheter, will occur in up to a third of patients with an indwelling catheter. CRT account for approximately 80% of upper extremity thrombosis, and pulmonary emboli have been detected in 15% of patients with symptomatic CRT. A systematic review and meta-analysis has reported rates of post-thrombotic syndrome (PTS) in an average of 15% of adults with upper extremity thrombosis. Retrospective studies of patients with upper extremity thrombosis report PTS rates between 7-47% and prospective studies report PTS rates of 15-25%. These studies contain a limited number of patients with catheter-related thrombosis. Presence of a catheter as the etiology of the upper extremity thrombosis is suggested to decrease the risk of PTS, but the outcomes of patients with catheter-related thrombotic events alone have not been well defined. Residual thrombosis after treatment and thrombosis of the axillary and/or subclavian vein increase the risk of PTS development; however, no prospective studies have evaluated if duration of anticoagulation in CRT influences the development of PTS. Patients with PTS have significantly worse quality of life and limb function, thus PTS is a patient important outcome to evaluate.

Anticoagulant treatment of CRT is used to improve patient symptoms and decrease recurrent thrombosis and pulmonary embolism. Low molecular weight heparin (LMWH, enoxaparin) has been the anticoagulant of choice for cancer patients with catheter-related thrombosis. Enoxaparin is the only LMWH FDA approved for treatment of acute venous thrombosis (enoxaparin product insert attached). However, in recent years, direct oral anticoagulants such as dabigatran, rivaroxaban, apixaban, and edoxaban have offered a more convenient alternative for anticoagulation. A randomized control trial and prospective cohort study of cancer patients with venous thromboembolism treated with a direct oral anticoagulant have been published. Two small studies have also been published in using rivaroxaban to treat CRT in cancer patients. Therefore direct oral anticoagulants have become part of clinical practice to treat cancer patients with thrombosis in addition to LMWH. The FDA package inserts can be found at the follow websites:

Rivaroxaban (Xarelto®): [http://www.accessdata.fda.gov/drugsatfda\\_docs/label/2011/202439s001lbl.pdf](http://www.accessdata.fda.gov/drugsatfda_docs/label/2011/202439s001lbl.pdf)

Apixaban (Eliquis®): [http://www.accessdata.fda.gov/drugsatfda\\_docs/label](http://www.accessdata.fda.gov/drugsatfda_docs/label)

[/2012/202155s000lbl.pdf](#)

Edoxaban (Savaysa®): [http://www.accessdata.fda.gov/drugsatfda\\_docs/label](http://www.accessdata.fda.gov/drugsatfda_docs/label)

[/2015/206316lbl.pdf](#)

Dabigatran (Pradaxa®): [http://www.accessdata.fda.gov/drugsatfda\\_docs/label](http://www.accessdata.fda.gov/drugsatfda_docs/label)

[/2011/022512s007lbl.pdf](#)

The catheter is removed if it is non-functioning or is no longer needed. The duration of anticoagulation in patients with catheter-related thrombosis has not been studied in a systematic fashion and is not standardized in clinical practice. A delicate balance exists between thrombosis and bleeding in cancer patients because cancer patients have 3 times higher risk of recurrent thrombosis and 2.5 times higher risk of major hemorrhage compared to non-cancer patients. Consensus guidelines have a weak recommendation for anticoagulation for 3 months after catheter removal in patients with upper extremity CRT (ACCP and ISTH guidelines attached). These recommendations are extrapolated from data on provoked lower extremity thrombosis, retrospective case series and two prospective cohort studies. Review of the literature reports treatment of catheter-related thrombosis ranging from catheter removal without anticoagulation to treatment with anticoagulation up to 6 months. In cancer patients, upper extremity CRT are often treated with anticoagulation for 4-6 weeks to balance the risks of thrombotic recurrence with bleeding. Additionally, extraction of the catheter removes an inciting factor for thrombosis which may allow for shorter duration of therapy. In a survey of MCW Heme/Onc physicians, treatment of patients with CRT ranged from 4 weeks to 3 months. A retrospective review of patients with hematologic malignancies from 2009-2011 found 85 patients with catheter-related thrombosis treated at MCW. Three patients (4%) were not treated for their CRT and 20 patients (24%) had the catheter removed only. Of the patients that underwent anticoagulation, the median total treatment duration was 42 days (range 3-1485 days). Of patients who had their catheter removed, the median treatment duration after catheter removal was 44 days (range 4-453 days). The retrospective study was not able to assess development of PTS due to lack of assessment as a part of routine practice. Overall, there is no standard treatment duration for patients with catheter-related thrombosis and 1 month of anticoagulation after catheter removal is within clinical practice at both locations. This multicenter prospective cohort pilot study project defines the duration of anticoagulation after catheter removal at one month to balance the risk of thrombosis with the risk of bleeding, patient cost and discomfort of injecting enoxaparin twice a day. The project will assess feasibility and obtain estimates of clinical outcomes including PTS, thrombosis recurrence, and bleeding. The feasibility outcomes will assess accrual, enrollment, and retention procedures. The data obtained from the pilot study will be used to provide sample size estimates for a larger definitive study. Additionally the

estimates will allow an appropriate comparison of duration of anticoagulation to be selected for a future randomized trial.

**Table 1:** Care of patients with CRT in practice vs. research protocol

	Typical Care Approach	Research protocol
Catheter removal	Not needed or malfunction	Not needed or malfunction
Anticoagulation Type	LMWH (enoxaparin or dalteparin)  Direct oral anticoagulant	Enoxaparin or direct oral anticoagulant
Duration of anticoagulation	1-3 months after catheter removal	1 month after catheter removal

A clinical scoring system or biomarker to predict recurrent catheter-related thrombosis in cancer patients do not exist. Currently patients are treated with anticoagulation for varying amounts of time based on local practice and extrapolation from clinical trials in lower extremity thrombosis. Development of biomarkers predictive of thrombosis would allow targeting of anticoagulation strategies in cancer patients at highest risk of thrombosis. The Ottawa score allows prediction of recurrent thrombosis in cancer patients and is based upon gender, history of thrombosis, cancer type and stage. The Khorana score integrates site of cancer, body mass index, and pre-chemotherapy platelet, leukocyte and hemoglobin levels to predict initial thrombosis. The Khorana score has not been evaluated as a predictor of thrombotic recurrence and will be assessed from clinical information at the time of CRT diagnosis. Validations of the Khorana score have also added biomarkers including D-dimer to expand the ability to detect high risk groups. Additionally, high levels of thrombin generation have been associated with increased risk of initial thrombosis in cancer patients. Elevated D-dimer and peak thrombin generation have been shown to be risk factors for recurrent thrombosis in non-cancer patients, but the association has not been evaluated in cancer patients. Tissue Factor Pathway Inhibitor (TFPI) functions to limit the activation of factor X by the tissue factor/Factor VIIa complex. TFPI has been shown to be a predictor of thrombosis with low levels of TFPI antigen associated with twice the risk of thrombosis. Platelet TFPI may also play a role in thrombotic risk as platelets accumulate at the site of injury. Platelet TFPI has not been assessed as a risk factor for thrombosis. Lastly, extracellular DNA released from neutrophils (NETs-neutrophil

extracellular traps) has been shown to form a scaffold for venous thrombosis in animal models. Circulating plasma free DNA is a marker for NET formation and will be assessed in our patients. Overall, the proposed project will evaluate novel assays (platelet TFPI, plasma free DNA, and thrombin generation with platelet-rich plasma) and apply techniques that predict incident thrombosis (Khorana score, D-dimer and thrombin generation with platelet-poor plasma) to predict the risk of recurrent thrombosis. Overall, identification of a biomarker to predict thrombosis would allow a personalized approach to anticoagulation that would avoid unnecessary bleeding risk, cost and lifestyle burdens in patients who do not require more prolonged courses of anticoagulation.

## **2. Study Objectives**

### **2.1 Feasibility Objectives:**

- 1) To determine the feasibility of a multicenter prospective cohort study of cancer patients with catheter-related thrombosis treated with 1 month of anticoagulation.
  - a. Feasibility will be defined as accrual of 56 patients in 1 year and 80% completion of PTS assessments
- 2) To determine the feasibility of obtaining plasma samples for biomarker analysis to predict recurrent venous thrombosis
  - a. Feasibility will be defined as obtaining 80% of plasma samples for biomarker analysis

### **2.2 Clinical Objectives:**

- 3) To determine the incidence of post-thrombotic syndrome, thrombotic recurrence and bleeding in cancer patients with catheter-related thrombosis treated with 1 month of anticoagulation
  - a. Success of the study will be defined as an incidence of post-thrombotic syndrome <20%.

## **3. Study Population**

The intended study population is any adult with cancer and catheter-related thrombosis. Children will not be included as the involved institutions do not care for children. No gender or ethnic group will be excluded or targeted in the study.

### **3.1 Study Sites**

- 1) BloodCenter of Wisconsin, Medical College of Wisconsin (MCW) and Froedtert Hospital, Milwaukee, Wisconsin

The primary study site will be in Milwaukee. Patients will be recruited from MCW/Froedtert Hospital. Laboratory testing will be completed at the BloodCenter of Wisconsin in the laboratory of [name].

- 2) Ohio State University, Wexner Medical Center, Columbus, Ohio

Ohio State University (OSU), Wexner Medical Center, will be a second site for the study. Patients from OSU will be followed with clinical assessments only.

### **3.2 Inclusion Criteria:**

1. Upper extremity venous thrombosis involving the axillary, subclavian, brachiocephalic, superior vena cava, and/or internal jugular veins associated with an indwelling catheter documented by ultrasound, CT or venography
2. Current hematologic or solid tumor malignancy undergoing chemotherapy, surgery, radiation or hormonal therapy for malignancy and bone marrow transplant if within 100 days of transplant
3.  $\geq 18$  years of age
4. Platelet count  $>50,000$
5. Creatinine clearance  $>30$  ml/min
6. Ability to provide informed consent

### **3.3 Exclusion Criteria:**

1. Underlying medical condition or chemotherapy requiring long-term anticoagulation
2. Known underlying higher risk thrombophilias including antiphospholipid antibody syndrome, antithrombin, protein C or protein S deficiencies, or homozygosity or compound heterozygosity for prothrombin G20210A or Factor V R506Q mutations.
3. Inability to remove venous catheter
4. Anticipated replacement of central venous catheter within 3 months after enoxaparin or direct oral anticoagulant therapy has been discontinued
5. Personal history of deep vein thrombosis or pulmonary embolism
6. Concurrent acute deep vein thrombosis of the leg or pulmonary embolism
7. Major bleeding or clinically relevant non-major bleeding in the preceding 60 days
8. Participation in another clinical trial that requires anticoagulation
9. Treatment with thrombolysis
10. Catheter removal  $>1$  month prior to enrollment

## 11. Use of anticoagulation >6 months prior to catheter removal

### 3.4 Study Discontinuation Criteria

Subjects may be removed from the study by the Investigator for any of the following reasons:

1. Subject's condition has changed after entering the study so that they no longer meet inclusion criteria, or develop any of the exclusion criteria.
2. Subject experiences an adverse event that warrants withdrawal from the study.
3. Principal investigator determines subject is non-compliant.
4. Subject requires placement of an alternate central venous catheter after discontinuation of enoxaparin or direct anticoagulant therapy.

### 3.5 Continuation of anticoagulation criteria

Participants will be continued on anticoagulation longer than one month after catheter removal if any of the following criteria exist:

1. Development of thrombosis other than the CRT
2. Extension of the catheter-related thrombosis (i.e. additional vein occlusion on imaging obtained for clinical reasons)

If an enrolled subject at MCW requires anticoagulation longer than 1 month after catheter removal, laboratory assessments will not be completed as the testing can be affected by the presence of an anticoagulant. The participant will not be removed from the study and will be followed for PTS outcomes.

## 4. Study Design

### 4.1 Study Overview

[figure not shown]

Figure 1 shows the overall study design of the multicenter prospective cohort of cancer patients with catheter-related thrombosis. Participants may be referred for screening at MCW in two possible mechanisms: participant contact study staff from information on CTSI FACT website or referral from treating Hematologist or Oncologist. At MCW, an EPIC report will be generated to identify people with CRT. The treating provider would then be contacted to determine if referral to the study was appropriate. Subjects at OSU will be referred from the treating Hematologist or Oncologist. A report generated in Epic will be used to identify people with CRT. The treating provider would then be contacted to determine if referral to the study was appropriate. Participants will be given printed information about the study (Appendix A) or verbal explanation using the informational flyer. Verbal consent will be obtained to be screened for participation and contacted by study personnel. Screening will be completed by BCW nurse coordinator (Script Appendix B; Screening form Appendix C). We aim to consent and enroll patients after diagnosis of catheter-related thrombosis and prior to catheter removal. Consent and enrollment (Visit 1) must occur prior to discontinuation of anticoagulation. Enrollment will be limited to patients undergoing anticoagulation with either enoxaparin or a direct oral anticoagulant at the discretion of the treating provider. The study will follow patients treated with anticoagulation for one month after catheter removal. Prior to discontinuation of anticoagulation, patients will be contacted via telephone to review study protocol, assess for bleeding, and arrange for Visit 2 in the following 1-2 weeks. Appendices D-H include the background information that will be collected. Visits 3 and 4 will occur 3 and 6 months after catheter removal, respectively. At visits 3 & 4, Medical history, cancer history, and medications will be updated (Appendices E-G). At each visit, participants will be assessed for post-thrombotic

syndrome using the modified Villalta scale (Appendix I) and functional limitation using the DASH questionnaire (Appendix J). At MCW, surveys will be administered by the TRU staff and physical examination will be completed by BCW nurse coordinator, [name]. At OSU, surveys will be administered by research coordinators trained to complete the assessment. Laboratory samples will be obtained for MCW participants only and processed as noted in section 5.6 and section 6.

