### **11.2 Statistical Analysis**

The incidence of PTS, thrombotic recurrence, major bleeding and clinically relevant non-major bleeding will be reported as proportions. These outcomes will be compared at 3 and 6 months using Chi-square or Fisher's exact tests. A Cox-proportional hazards model will be utilized to calculate the risk of PTS and thrombosis recurrence. Chi-square or Fisher's exact tests will be used to determine if clot presentation or location predicts PTS or thrombotic recurrence. Agreement between the DASH and QuickDASH scales will be assessed using the intraclass correlation coefficient. To compare the discriminating ability of the DASH and QuickDASH on the level of PTS, receiver operating curves will be developed using the scale scores at 6 months as the test variable and dichotomized PTS assessment as the classifying variable. Levels of D-dimer, thrombin generation, and TFPI will be reported as means. Logistic regression will evaluate if D-dimer, thrombin generation or TFPI levels at 1 month or % change from baseline predict thrombotic recurrence. Where necessary, for parametric assumption, we will employ appropriate transformations with justifications. For example, the log of some of the biomarkers data may be used if the data range is >1000. Statistical

significance will be determined with  $p < 0.05$ . SAS version 9.13 and JMP 10 Statistical software will be employed for data analysis.

An interim analysis will be completed after 20 patients complete 6 months of follow-up. The interim analysis will allow assessment of thrombotic recurrence by the DSMC.

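### Because entry is allowed up to a month after catheter removal and a recent bleed bars it, plain proportions counted from removal would understate bleeding, probably by a small amount, and recurrence less certainly

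*Combined protocol and SAP*

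**What the plan says.** **Entry.** Section 4.1 states an intention: "We aim to consent and enroll patients after diagnosis of catheter-related thrombosis and prior to catheter removal". Section 5.1 repeats it. The binding rules are looser. Section 4.1 requires only that "Consent and enrollment (Visit 1) must occur prior to discontinuation of anticoagulation", and exclusion 10 in section 3.3 turns a patient away only for "Catheter removal $>1$ month prior to enrollment".

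**Conditions at entry.** Section 3.3 excludes patients with "Major bleeding or clinically relevant non-major bleeding in the preceding 60 days" (exclusion 7), "Concurrent acute deep vein thrombosis of the leg or pulmonary embolism" (exclusion 6) and "Personal history of deep vein thrombosis or pulmonary embolism" (exclusion 5). Extension of the original catheter-related thrombosis (CRT) is not among the exclusions.

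**Clock.** Section 4.1: "Visits 3 and 4 will occur 3 and 6 months after catheter removal, respectively". The regimen studied is the month of anticoagulation after removal (sections 1 and 5.2).

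**Analysis.** Section 11.1.3 lists recurrent thrombosis and bleeding as secondary endpoints; the bleeding categories are those of exclusion 7. Under section 11.2 these outcomes "will be reported as proportions" and are compared at 3 and 6 months. A Cox model is planned for PTS and recurrence, but not for bleeding. Section 11 gives no time origin for these events, no entry time for the risk set, and no separate count of patients enrolled after removal.

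**The concern.** Suppose a patient consents 25 days after removal. Had that patient bled on day 10, exclusion 7 would have kept them out. The 60-day look-back is longer than the one-month entry window, so any qualifying bleed between removal and consent bars entry. The patient cannot contribute an event from days 0 to 25 but counts as fully observed in a proportion that runs from removal. This is left truncation, and ignoring it pushes the estimate down whenever bleeds can occur in that gap. The rule that entry must precede the end of anticoagulation works the same way, because a patient whose treatment stopped early on account of a bleed could not enrol.

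Section 1 says the pilot's estimates will be used to size a definitive study and to choose the duration it compares. Bleeding in the anticoagulated month after removal is central to the case for a short course, and it is the period that late entrants are selected to have passed without a bleed.

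**Working it through.** **The plan's own figures.** The documents give no figure for late entry. Section 4.3 gives precision for 50 completers: 80% completion corresponds to 66-90%. The exact 95% interval for 40/50 is 66.3-90.0%, which matches. The same exact method is used below for sampling error.

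**Inputs from the documents.** Entry up to 1 month after removal (3.3); follow-up to 6 months from removal (4.1, 5.5); 50 completers (4.3); recurrence of 20% reported in other studies (10.4).

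**Assumed, because the documents do not give them.** A 6-month bleeding risk R = 10%; a share f of 25% or 50% enrolling after removal; their entry times uniform over the month; and m, the risk falling within month 1, at a constant hazard within that month.

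**Formula.** The average chance of being event-free at a uniform entry time is S = m / [-ln(1 - m)]. Per patient eligible at removal, D = 1 - f(1 - S) are enrolled and 1 - R remain event-free at 6 months. All of the latter can enrol, so

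observed proportion = 1 - (1 - R)/D.

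**Bleeding, R = 10%**

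| Timing of bleeds | m | S | D, f = 25% | Observed | D, f = 50% | Observed |
|---|---|---|---|---|---|---|
| Constant rate over 6 months | 1 - 0.9^(1/6) = 0.0174 | 0.9913 | 0.9978 | 9.8% | 0.9956 | 9.6% |
| Half in month 1 | 0.05 | 0.9748 | 0.9937 | 9.4% | 0.9874 | 8.9% |
| All in month 1 | 0.10 | 0.9491 | 0.9873 | 8.8% | 0.9746 | 7.7% |

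For example, with half in month 1 and f = 50%: 1 - 0.90/0.9874 = 0.089.

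**Recurrence, R = 20%, half of events in month 1.** Only events that bar entry enter S.
- If every month-1 event barred entry (m = 0.10), the observed figure would be 1 - 0.80/0.9873 = 19.0% for f = 25% and 1 - 0.80/0.9746 = 17.9% for f = 50%. This is an upper bound on the loss under these assumptions, because extension of the CRT does not bar entry.
- If half of those events were extensions and were counted (m = 0.05), it would be 1 - 0.80/0.9937 = 19.5% and 1 - 0.80/0.9874 = 19.0%.

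**Does delayed entry repair it?** In a simulation of 400,000 patients (true 6-month risk 20%, half entering late, one third of events in month 1, every early event barring entry), the plain proportion was 18.7% and the delayed-entry estimate 20.0%.

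**Against sampling error.** The exact 95% interval for 5/50 is 3.3-21.8%, that is, 6.7 points below and 11.8 above the 10% estimate. The losses in the bleeding table run from 0.2 to 2.3 points.

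**The case against.** **Late entry is a fallback.** This stands. The stated aim is to enrol before removal, and if that mostly happens the bias is a fraction of a point. A reader might infer a much larger effect by supposing that everyone enrols late: with all bleeds in month 1, a true 10% would then appear as 5.2%. That contradicts the stated aim, and no figure in the protocol supports it.

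**The origin is inferred.** This also stands. A reader might take section 11.2 to say that proportions run from removal. It does not; that reading comes from the visit schedule and the 3- and 6-month comparisons. Section 9.7 puts anticoagulation at 0 to 6 months before removal, so some on-study bleeding may precede removal. If counting starts at consent, the result is a different quantity: risk conditional on reaching consent event-free, with late entrants' early exposure omitted. The need to state the origin remains.

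**Recurrence is less affected than bleeding.** Correct. A reader might infer that both endpoints are biased alike. Exclusions 5 and 6 act through new leg DVT or PE, whereas sections 3.5 and 10.4 group CRT extension with new thrombosis. Whether an extension before consent counts is not stated, so the size for recurrence is not established. The planned Cox model covers recurrence, but without an entry time it does not settle the matter.

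**The bias is small beside the noise, and the endpoints are secondary.** Both are true. Nothing here shows that the feasibility criteria or the PTS criterion of under 20% are affected. The bias does, however, have a fixed direction, and enrolling more patients would not remove it.

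**Conclusion.** The point holds for bleeding, provided events are counted from removal: the entry rules remove patients who bleed early, section 11.2 does not allow for it, and the resulting bias is downward. For recurrence it holds only through new leg DVT or PE and is smaller and less certain.

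No single corrected figure can be given. At an assumed 10% bleeding risk with 25% to 50% entering late, uniformly over the month, the loss is about 0.2 to 0.4 points at a constant rate, 0.6 to 1.1 points with half of bleeds in month 1, and 1.2 to 2.3 points with all of them there. None of this would by itself overturn a conclusion from 50 patients. It is an inexpensive improvement to estimates meant to feed a later trial; the documents do not support reading it as a serious distortion of this one.

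**What to change.** In section 11.2:

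1. State that catheter removal is time zero for post-removal bleeding and recurrence.
2. Estimate the cumulative incidence of each with delayed entry, every patient joining the risk set at the later of removal and consent.
3. Report how many patients enrolled before and after removal.
4. Give a sensitivity estimate limited to those enrolled on or before removal.

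This takes a few sentences and leaves enrolment, treatment and visits unchanged. The dates should be available: removal sets the visit schedule, consent is a study procedure, and section 8.2 lists the dates of bleeding and recurrence.

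The change is not free. Intervals will be wider, and if few patients enrol before removal, few are at risk in the first days and the early part of the curve becomes unstable. The counts in item 3 will show whether that has happened. Delayed entry also does not correct the selection that the 60-day bleeding rule makes among patients enrolled before removal; that is a limit on whom the results describe and should be stated as such.
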